### Intervention

The intervention will be carried out identically at all sites and will be comprised of 31 sessions at the subjects' trial site, including 4 assessment sessions (pre, mid, immediately post treatment, and 8 weeks post-treatment), 3 exoskeleton fitting/training sessions, and 24 intervention sessions. The interventions at each site will be administered by a PT experienced in locomotor training for individuals with SCI. Parker Hannifin will provide exoskeleton-specific training at each site, in order to ensure safe, effective implementation and use of the exoskeletons. A summary of each session's activity and measurements follows:

- Session 1: Informed consent and pre-treatment health and neurological assessment, including PT evaluation and Dexa Scan (x-ray picture of the bone) of the distal femur and proximal tibia locations, and drawing about 2 teaspoons (9.5 mL) of blood to check A1C (measures the amount of hemoglobin in the blood that has glucose attached to it) and Lipid Panel to measure cholesterol levels (lasting 4 hrs).
- Sessions 2-4: Exoskeleton fitting, adjustment, and training sessions (3 sessions per week lasting 1.5 hours per session)
- Sessions 5-16: Exoskeleton treatment consisting of walking in the exoskeleton during a 1.5-hr session, with breaks as needed, and with sit-to-stand, turning, and stand-to-sit maneuvers as appropriate (3 sessions per week lasting 1.5 hours). Note that sessions 15 and 16 are additionally used for assessment of the mobility provided by the exoskeleton.
- Session 17: Mid-treatment health and neurological assessment (lasting 3-4 hours).
- Sessions 18-29: Exoskeleton treatment consisting of walking in the exoskeleton during a 1.5-hour session, with breaks as needed, and with sit-to-stand, turning, and stand-to-sit maneuvers as appropriate (3 sessions per week lasting 1.5 hours per session). Note that sessions 28 and 29 are also used for assessment of the mobility provided by the exoskeleton.

- Session 30: Post-treatment health and neurological assessment, within 3 days of session 29, including Dexa Scan (x-ray picture of the bone) of the distal femur and proximal tibia locations, and 2 teaspoons (9.5 mL) of blood to check A1C (measures the amount of hemoglobin in the blood that has glucose attached to it) and Lipid Panel to measure cholesterol levels (lasting 3-4 hours).
- Session 31: Follow-up health and neurological assessment, including Dexa Scan (x-ray picture of the bone) of the distal femur and proximal tibia locations, and 2 teaspoons (9.5 mL) of blood to check your A1C (measures the amount of hemoglobin in the blood that has glucose attached to it) and Lipid Panel to measure cholesterol levels, 8 weeks following session 30 (lasting 3-4 hours).

Women of child bearing potential will have a urine pregnancy test at baseline, and in sessions 17, 30 and 31.

### Outcome Measures

The various measures employed in Study 1 are summarized below:

#### Measures assessing physiological (i.e., health) effects:

- DXA: Assessment of changes in BMD over treatment course. Scans will be taken at the distal femur and proximal tibia locations.
- Spasticity rating: MAS, used to assess changes in degree of spasticity over course of treatment. Physical Therapy will assign a gross MAS score for the upper and lower extremities immediately after exoskeleton use as well as on the following day, in order to characterize acute and non-acute effects of exoskeleton use on spasticity.
- SCI-SET: 7-day recall self-report questionnaire that takes into account the effects of spasticity on daily life in people with SCI. Subjects will complete SCI-SET at treatment-start, at mid-point, immediately post-treatment, and at an 8-week post-treatment follow-up.
- Weight: Subjects will be weighed pre-treatment, at treatment midpoint, following treatment, and at an 8 week post-treatment follow-up.
- Subject self-report health questionnaire, including questions regarding pain, spasticity, bowel and bladder function, skin, and well-being.

#### Measures assessing neurological or functional recovery:

- International Standard for Neurological Classification of SCI (ISNCSCI, R2011). Neurological exams will assess status of neurological recovery. Since inclusion criteria restrict inclusion to chronic injury (i.e., at least 6 months post-injury, preferably at least 1-year post-injury), significant changes in neurological testing would presumably be a result of treatment. This exam will include manual muscle testing (MMT) for subjects with incomplete injury.
- For subjects who are poorly-ambulatory: FIM gait score, WISCI-II rating, 10MWT, and TUG test, all while the subject is not wearing the exoskeleton.
- FR test will be performed while subject is sitting to assess potential changes in trunk control and/or strength.
- Borg Reported Perceived Exertion Scale (BRPE)

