### Study Outline

Study 1, as described herein, will assess the three hypotheses, i.e., health benefit, neurological recovery, and mobility benefits, in the context of regular dosing of exoskeleton walking in a clinical setting. These studies will be conducted at three study sites, Vanderbilt University Medical Center in Nashville TN, the James A. Haley Veterans Hospital in Tampa FL, and the Mayo Clinic in Rochester MN. All study sites will conduct an identical study protocol. The study will involve 24 non-ambulatory and poorly-ambulatory individuals with incomplete and complete SCI (i.e., 8 subjects at each site). In this study, “poorly ambulatory” is defined as persons with functional independence measure (FIM) gait score of 2 to 6 who may be able to walk short distances with or without braces and stability aid, or may be able to walk with assistance of one person, but whose primary means of mobility is a manual or power-operated wheelchair. Of the 24 individuals, half will be individuals with motor-complete injuries (i.e., American Spinal Injury Association Injury Scale, AIS, A or B), and half with motor-incomplete injuries (i.e., AIS C or D). As described subsequently in the Study Procedures section, the study will assess the therapeutic and functional effects of exoskeleton walking over an 8-week period of treatment, where the treatment consists of 3 walking sessions per week, each approximately 1.5 hours in duration for a total of 24 walking sessions. Therapeutic effects will be assessed via a number of measurements recorded primarily at study start, at the 4-week study midpoint, at the 8-week completion of treatment, and in a follow-up session, 8 weeks following the conclusion of treatment. Among the primary measurements to be used to assess secondary health benefits are dual-energy X-ray absorptiometry scans (DXA) to assess bone mineral density (BMD); Modified Ashworth scale (MAS) ratings and Spinal Cord Injury Spasticity Evaluation Tool (SCI-SET) to assess effect on spasticity; body mass to assess BMI; and a self-report questionnaire to assess effect on pain, spasticity, bowel and bladder function, skin, and well-being. Neurological effects for non-ambulatory subjects will be assessed via neurological examination and the functional reach (FR) test. Neurological effects for poorly-ambulatory subjects will additionally be assessed via the Functional Independence Measure gait score (FIM-G), the Walking Index for Spinal Cord Injury II (WISCI-II), the Ten Meter Walk Test (10MWT), and the Timed Up and Go (TUG) test, all measured while the subject is not wearing the exoskeleton. The level of mobility provided by the exoskeleton for both motor-complete and motor-incomplete injuries will be assessed by use of the FIM-G, WISCI-II, 10MWT, Six-Minute Walk Test (6MWT), TUG test, and Borg Rating of Perceived Exertion (BRPE), all measured while the subject is wearing the exoskeleton.

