#### **4.0 Inclusion/Exclusion Criteria**

##### Inclusion Criteria:

- Age 18 years or older.
- Size and limb proportions capable of fitting in the exoskeletal device :
  - Height between 1.55 m (5 ft, 1 in) and 1.92 m (6 ft, 3 in).
  - Femur length between 37.5 cm (15 in) and 43.125 cm (17.25 in).

- Body mass no greater than 114 kg (250 lb).
- Non-ambulatory or poorly-ambulatory. In this study, “non-ambulatory” is defined as a person who cannot walk, or is classified with a Functional Independence Measure (FIM) Gait score 1; “poorly ambulatory” is defined as a person with FIM Gait 2- 6, who may be able to walk short distances with or without braces or stability aid, or may be able to walk with assistance of one person, but whose primary means of mobility is a manual or power-operated wheelchair.
- Sufficient upper extremity strength and coordination to balance using appropriate stability aids, such as a rolling walker or forearm crutches, during exoskeleton walking.
- Present with SCI and NLI C5 or lower, with AIS A, B, C or D (as per the International Standard for Neurological Classification of SCI, ISNCSCI), who are non-ambulatory or poorly ambulatory.
- Chronic SCI: at least 6 months post-injury, and preferably post-injury more than 1 year.
- Sufficient bone health for walking with full weight-bearing without undue risk of fracture, as determined by each subject’s personal medical doctor, and approved by each site’s medical supervisor.
- Passive range of motion (PROM) at shoulders, trunk, upper extremities and lower extremities within functional limits for safe gait and use of appropriate assistive device/stability aid.
- Skin intact where interfacing with robotic device.
- MAS for spasticity score 3 or less in lower extremities.
- Blood pressure and heart rate within established guidelines for locomotor training:
  - At rest: systolic 150 mmHg or less, diastolic 90 mmHg or less, heart rate 105 bpm or less.
  - During exercise: systolic 180 mmHg or less, diastolic 105 mmHg or less, heart rate 145 bpm or less.
- Ability to tolerate an upright standing position for 20 min, passive or active, without being lightheaded or having a headache.

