## 6.0 Study Procedures

### Design:

This study will include 24 non-ambulatory or poorly-ambulatory individuals with chronic SCI, i.e., at least 6 months post-injury, 12 with complete and 12 with incomplete SCI, to assess the mobility and therapeutic benefits resulting from exoskeleton use in a clinical setting. Changes in physiological and neurological status will be assessed via measurements taken pre-, mid-, and post- the 8-week intervention, as well as 8 weeks post-treatment. At all study sites, subject enrollment will begin following IRB approval, with 8 subjects enrolled at each of the 3 sites. Following IRB approval and enrollment, the study is expected to occur over an 18-month period. The treatment for each subject will consist of 31 sessions spanning 18 weeks in total, comprising a combination of 4 assessment, 3 training, and 24 treatment sessions. The 24 treatment sessions each consists of approximately 1 hour of walking in the exoskeleton, although 1.5 hours are allotted to account for donning/doffing, measurement of vital signs, skin checks, etc., and will be delivered 3 times per week over an 8-week period.

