#### Data Analysis

Table 1 lists the relationships between the outcome measures and each hypothesis. Given that each patient is in a chronic stage of injury (i.e., spontaneous changes in health and neurological status are unlikely or minimal), the investigators assume that any statistically significant change in the outcome measures between pre- and post-treatment will have resulted from treatment. Since all measures are quantitative, including the self-report and SCI-SET, testing the respective hypotheses entails testing the extent to which the pre- and post-treatment means, of respective measurements across all subjects, are different. As such, the investigators will employ paired-sample t-tests to test the extent to which pre- and post-treatment means are statistically different, by employing a 95% confidence level in the analysis, unless results indicate a more appropriate confidence level for a given set of data. In addition to using paired t-tests for validating differences in means, and establishing associated confidence levels in those differences, analysis of variance (ANOVA) methods will be employed when determining statistical significance of differences in means between multiple data sets, with 95% confidence levels. Specifically, ANOVA will be used when assessing differences in means between pre-, mid-, post-, and 8-week follow-up measurements. In addition to analyzing results across all subjects, more meaningful results will be provided by separating the subject population into appropriate groups, such as: motor-complete and motor-incomplete individuals; non-ambulatory and poorly-ambulatory ones; individuals with tetraplegia and those with paraplegia; persons with upper paraplegia and those with lower paraplegia; etc. For example, measures associated with walking while not wearing the exoskeleton will only be recorded for poorly-ambulatory individuals; neurological recovery is not expected for individuals with motor-complete injuries (while perhaps possible, such recovery is not hypothesized here); and individuals with tetraplegia are less likely to achieve walking speeds and levels of independence commensurate with community ambulation, relative to individuals with paraplegia. For these groups, ANOVA techniques will be employed to assess differences in

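### Pre-post change is credited to treatment because injuries are chronic, but entry is open from 6 months post-injury and no named analysis uses time since injury

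*Protocol*

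**What the plan says.** **Attribution.** The Data Analysis section of the protocol (6.0) reasons that "spontaneous changes in health and neurological status are unlikely or minimal" in chronic injury, and on that ground "the investigators assume that any statistically significant change in the outcome measures between pre- and post-treatment will have resulted from treatment". This is the firm version, and it covers all outcomes. The section on measures of neurological or functional recovery says the same of the neurological examination in softer terms: "significant changes in neurological testing would presumably be a result of treatment".

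**Eligibility.** The inclusion criteria (4.0) read "Chronic SCI: at least 6 months post-injury, and preferably post-injury more than 1 year". The Design section keeps only the lower limit: "This study will include 24 non-ambulatory or poorly-ambulatory individuals with chronic SCI, i.e., at least 6 months post-injury". The neurological measures section repeats both thresholds ("at least 6 months post-injury, preferably at least 1-year post-injury") in the sentence that justifies attribution.

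**Analysis.** The subgroups named in Data Analysis are motor completeness, ambulatory status, tetraplegia against paraplegia, and upper against lower paraplegia. The list is left open, and time since injury is not on it. The SAP names a Kolmogorov–Smirnov check, medians with IQR and a Wilcoxon rank-sum test. It mentions no subgroup, covariate or sensitivity analysis.

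**The concern.** The documents describe no control group, and there is one pre-treatment assessment, at session 1. The step from a pre-post difference to a treatment effect therefore rests on the premise that nothing would have changed without treatment. For spontaneous recovery, that premise rests on time since injury alone. The protocol prefers more than 1 year, which suggests that its authors did not regard the two periods as equally safe, yet nothing enforces the preference or limits how many people enter earlier.

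Hypothesis 2, on neurological or functional recovery, is the most exposed. It expects recovery in some participants, mainly those with incomplete injuries, who make up 12 of the 24. If several of those 12 are in their first year, natural improvement would be reported as a result of the exoskeleton, and no planned display would let a reader see it.

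**Working it through.** The plan gives no figure to reproduce: there is no effect size, standard deviation or assumed rate of spontaneous change. The check compares the passages, then does the calendar arithmetic, then gives an illustration on assumed inputs.

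**1. Does eligibility secure the premise?** The attribution rule needs spontaneous change to be negligible in everyone analysed. The binding entry rule is 6 months; the 1-year threshold is a preference. Between 0 and 24 participants could be at 6 to 12 months.

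**2. Can the whole study fall inside the first year?** Inputs: entry at 6 months, about week 26; participation of 18 weeks (Design section).
- End of follow-up: 26 + 18 = week 44, which is before week 52.
- Latest entry with every assessment inside the first year: 52 − 18 = week 34.
- The pre-post contrast is shorter. Session 30 falls at about week 11 of the schedule, so entry at week 26 gives a post-treatment assessment at about 26 + 11 = week 37. Anyone entering by about 52 − 11 = week 41 has the full pre-post interval inside the first year.

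**3. What would spontaneous change do to the planned test?** Assumptions, none of them from the documents: zero treatment effect; the protocol's paired t-test, two-sided at 0.05; only first-year participants drift, by 0.5 or 1.0 SD of the change score; they make up 25% or 50% of the sample. Probability of a significant improvement (100,000 simulated trials per cell):

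| First-year share | Drift | n = 24 | n = 12 |
|---|---|---|---|
| any | 0 | 2.5% | 2.5% |
| 25% | 0.5 SD | 7.7% | 5.5% |
| 50% | 0.5 SD | 19.6% | 11.1% |
| 25% | 1.0 SD | 16.5% | 9.0% |
| 50% | 1.0 SD | 55.8% | 27.0% |

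The n = 12 column corresponds to the motor-incomplete group. Under the Data Analysis rule, every such result would be credited to treatment. The table shows direction and sensitivity only. With no first-year participants, or no drift, the excess is zero.

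**4. Does any named analysis expose it?** No. Time since injury is not listed among the subgroups in Data Analysis, and the SAP lists no subgroups.

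**The case against.** **A minimum with a preference is not a contradiction.** This stands. A reader might infer that admitting people at 6 months breaches the protocol's own rule. It does not: both thresholds are stated openly and are compatible. The preference also works against early enrolment, and the documents do not show that anyone entered at 6 to 12 months.

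**The subgroup list is open.** True, so a split by time since injury is permitted. It is not specified, and the attribution rule applies whether or not it is done.

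**The 8-week post-treatment follow-up is a partial check.** Continuing natural recovery would tend to show as further gain after treatment stops. That is useful, but the rule attributes pre-post change without reference to what follows, and loss of a treatment effect could mask continuing recovery.

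**One or two individual gains prove nothing under this plan.** Correct. The protocol compares means and the SAP compares medians. The chance that at least one participant improves spontaneously is therefore the wrong measure, and none is given here.

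**Restricting to more than 12 months does not rescue attribution.** Also correct. With one arm and one baseline, practice effects and regression to the mean remain for everyone. The restricted group may also be very small: with five participants, the smallest two-sided p-value from a paired signed-rank test is 2/2⁵ = 0.0625. A requirement that the effect also be significant in that group would be unworkable.

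**Conclusion.** The concern holds in a limited form. Significant pre-post change is attributed to treatment on a premise that the entry criteria do not secure for participants at 6 to 12 months, and no named analysis would reveal the consequence. All of a participant's assessments can fall in the first year if entry is by about week 34 post-injury. The exposure is greatest for neurological and off-device walking outcomes in the 12 motor-incomplete participants.

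The size cannot be determined from the documents. It depends on how many participants entered at 6 to 12 months and on how much they would have changed untreated, and neither is given. A reader might go further and infer that reported recovery is spontaneous, or that recovery seen beyond 12 months must be due to treatment. The documents support neither inference. This is an inexpensive improvement that narrows what the trial may conclude; it does not invalidate the study.

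**What to change.** 1. Report time since injury at session 1, including the number at 6 to 12 months, overall and among motor-incomplete participants. If that number is zero, one sentence settles the point.
2. Add a sensitivity analysis of change in ISNCSCI/MMT and in off-device walking measures, restricted to participants more than 12 months post-injury. Show estimates with confidence intervals beside the all-participant result, and judge direction and size rather than significance. The SAP is written in the past tense, so label this post hoc if the data have already been analysed.
3. In the neurological measures and Data Analysis sections, replace the attribution wording with *change observed during treatment*. State that spontaneous recovery is not excluded for participants at 6 to 12 months, and that practice effects and regression to the mean remain possible for all.

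Eligibility and visits stay as they are. Time since injury is already needed to apply the entry criterion, so the work is one extra display and revised wording. The cost is small subgroups with wide intervals and a more cautious statement on neurological recovery.

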#### Measures assessing level of mobility enabled by the exoskeleton to include the following, all measured while subject is using the exoskeleton:

- The 10MWT as a measure of gait speed.
- The TUG test measures ability to independently sit, stand, walk, turn, and return to sitting. The TUG test will be used as a measure of mobility independence.

- The 6MWT measures gait speed over a six-minute period. This test provides a controlled measure of endurance, and provides a secondary measure of gait speed.
- The BRPE measures perceived exertion during walking and will be assessed in this protocol during the 6MWT.

Additional measures taken during each session will include:

- Vital signs at start of each session (blood pressure and heart rate)
- Number of steps taken during each training session (measured by exoskeleton)
- Monitoring of skin integrity at exoskeleton contact points, following each session

Schedule of Assessments

The study will include 4 primary assessments characterizing health and neurological effects of exoskeleton use, in addition to 2 primary assessments characterizing level of mobility provided by the exoskeleton. The assessments characterizing potential health include DXA, MAS, SCI-SET tests, weight, and a self-report questionnaire. The assessments characterizing potential neurological or functional recovery include the MMT and FR tests, and for poorly-ambulatory subjects, also include the FIM-G, WISCI-II, 10MWT, and TUG tests, all performed without the exoskeleton. This battery of assessments is expected to require 3-4 hours, and will occur 4 times during the study as follows: pre-treatment (at study start, session 1), mid-treatment (after 4 weeks of treatment, session 17), post-treatment (after 8 weeks of treatment, session 30), and 8 weeks post-treatment (session 31). Note that DXA will not be measured at mid-treatment, in order to mitigate associated costs, since an 8-week interval is a short enough period of time relative to characteristic time scales associated with changes in BMD. Note that treatment will not occur on these assessment days, i.e., the exoskeleton will not be used on these days. Finally, the MAS will be administered on these 4 days, and also on 3 additional days, each immediately following exoskeleton use associated with a treatment session, at the start, mid-point, and end of treatment.

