**TABLE 1: Hypotheses and measures associated with Study 1**

Hypothesis	Method of Measurement/Testing
Decreased BMI	Body mass (weight) at baseline, treatment midpoint, post-treatment, and at 8 week post-treatment follow-up
Changes in BMD	DXA at baseline, post-treatment, and at 8 week post-treatment follow-up
Improved bowel and bladder function	Self-report at baseline, treatment midpoint, post-treatment, and at 8 week post-treatment follow-up
Reduced spasticity	MAS and SCI-SET at baseline, treatment midpoint, post-treatment, and at 8 week post-treatment follow-up
Reduction in pain	Self-report at baseline, treatment midpoint, post-treatment, and at 8 week post-treatment follow-up
Enhanced well-being	Self-report at baseline, treatment midpoint, post-treatment, and at 8 week post-treatment follow-up
Neurological recovery (complete SCI)	ASIA neurological exam and FR at baseline, treatment midpoint, post-treatment, and at 8 week post-treatment follow-up
Neurological recovery (incomplete SCI)	ASIA neurological exam, FR, and MMT at baseline, treatment midpoint, post-treatment, and at 8 week post-treatment follow-up
Functional recovery (poorly-ambulatory)	FR, MMT, FIM-G, WISCI-II, TUG, 10MWT, and BRPE at baseline, treatment midpoint, post-treatment, and at 8 week post-treatment follow-up
Community mobility	FIM-G, WISCI-II, TUG, 10MWT, and 6MWT and BPPE relative to published recommendations for community ambulation

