Statistical Analysis Plan

Mobility and Therapeutic Benefits resulting from Exoskeleton Use in a Clinical Setting (SC140121 Study 1)

NCT03082898

[name]

H. Fort Flowers Professor of Mechanical Engineering

Professor of Electrical Engineering

Professor of Physical Medicine and Rehabilitation

[name]

[name]

[name]

Statistical Analysis Plan

Normality of data was determined for each measure by a Kolmogorov–Smirnov (KS) test. All measures were determined to be non-normally distributed, and as such are represented by median and IQR rather than mean and standard deviation. Differences in medians in all measures were tested using a Wilcoxon rank-sum test, with confidence levels for each given by corresponding p values.

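### No value is set for an off-device 10MWT or TUG that a participant attends but cannot complete, so either documented test can bias these two functional-recovery measures

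*Protocol*

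**What the plan says.** The protocol's list of neurological and functional recovery measures includes: "For subjects who are poorly-ambulatory: FIM gait score, WISCI-II rating, 10MWT, and TUG test, all while the subject is not wearing the exoskeleton". The Schedule of Assessments places this battery at four visits: pre-, mid- and post-treatment, and 8 weeks after treatment. Table 1 makes the two timed tests part of the functional-recovery hypothesis for poorly-ambulatory participants: "FR, MMT, FIM-G, WISCI-II, TUG, 10MWT, and BRPE at baseline, treatment midpoint, post-treatment, and at 8 week post-treatment follow-up".

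The inclusion criteria define poorly-ambulatory as FIM gait 2 to 6 with a wheelchair as the main means of mobility. Such a person "may be able to walk short distances with or without braces or stability aid", or "may be able to walk with assistance of one person". Under the in-exoskeleton measures the protocol describes the scales: "The 10MWT as a measure of gait speed" and "The TUG test measures ability to independently sit, stand, walk, turn, and return to sitting".

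Protocol Data Analysis treats every measure as quantitative. It compares pre- and post-treatment means by paired t-test and the four visits by ANOVA. The SAP reports medians and states: "Differences in medians in all measures were tested using a Wilcoxon rank-sum test". Neither document mentions a zero speed, time cap, worst rank, completion status or missing-data rule for a test that was attempted but not finished.

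**The concern.** A person who walks only with help, or only a short way, may be unable to finish 10 m or an independent stand-walk-turn-sit sequence at one visit and manage it at another. Moving from unable to able is the kind of recovery that hypothesis 2 looks for; moving the other way is the loss that a fair comparison must count. If only measured values are analysed, these participants are lost or half lost, and the comparison rests mainly on those who could walk at both visits. The group is small: 24 participants in all, of whom only the poorly-ambulatory are tested off the device. A few people can therefore decide the 10MWT and TUG results.

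This is a separate matter from FIM gait 1 participants, who are not given these tests, and from the in-exoskeleton tests.

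**Working it through.** **What can be reproduced.** The plan gives no power, effect size, SD or number of poorly-ambulatory participants. Only the counts can be checked: 3 × 8 = 24 = 12 + 12. All speeds below (m/s, 10MWT) are assumptions that show the mechanism; they do not estimate its frequency.

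**1. Protocol test: paired t-test, t = mean change / (SD/√n).**

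Assume 7 participants complete both visits, with changes 0.06, 0.05, 0.04, −0.01, 0.07, 0.08, 0.02. Three others walk at 0.15, 0.20 and 0.25 at baseline and are unable after treatment.

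- Complete pairs only: sum 0.31, mean 0.31/7 = 0.044, SD 0.031, SE 0.031/√7 = 0.0117, t = 3.78 on 6 df, p = 0.009.
- All ten, inability = 0 m/s: sum 0.31 − 0.60 = −0.29, mean −0.029, SD 0.123, SE 0.123/√10 = 0.0389, t = −0.75 on 9 df, p = 0.47.
- Adding only the participant who loses 0.15: sum 0.16, mean 0.16/8 = 0.020, SD 0.0745, SE 0.0263, t = 0.76 on 7 df, p = 0.47.

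The sign of the mean reverses and the apparent significance disappears; one such participant is enough to remove the significance. The exact signed-rank test, which is in neither document, moves from p = 0.031 to 1.0. The median change stays positive (0.05, then 0.03).

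In the other direction, take completers' changes 0.03, −0.02, 0.04, −0.01, 0.05, −0.06, 0.02: mean 0.05/7 = 0.007, p = 0.65. Add three who go from unable to 0.15, 0.20 and 0.25: mean (0.05 + 0.60)/10 = 0.065, p = 0.07. The estimate changes a great deal, but 0.05 is not crossed.

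**2. SAP test: rank-sum on the values available at each visit.**

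- Assume seven walkers at 0.20, 0.25, …, 0.50, each gaining 0.03, and three who are unable at baseline and walk at 0.10 to 0.15 afterwards. The baseline median is the 4th of 7 = 0.35. After treatment the three newcomers rank lowest, so the median of 10 is (0.28 + 0.33)/2 = 0.305. The median falls although nobody worsened. With 0 m/s for inability at baseline, it rises from (0.25 + 0.30)/2 = 0.275 to 0.305.
- One newcomer can suffice. Assume eight walkers at 0.10, 0.15, 0.20, 0.25, 0.30, 0.40, 0.50, 0.60 with gains 0.02, 0.01, 0.03, 0.02, 0.01, 0.03, 0.02, 0.02, and one new walker at 0.05. Available-value medians go from (0.25 + 0.30)/2 = 0.275 to 0.270 (5th of 9). Zero-scored, they go from 0.250 to 0.270.
- With four newcomers (0.05, 0.08, 0.10, 0.12), available-value medians fall from 0.275 to (0.16 + 0.23)/2 = 0.195, although all 12 improved. Zero-scored, the medians are 0.175 and 0.195, mean change 0.51/12 = 0.043, signed-rank p = 0.0005.

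**3. How often the sign would be wrong.** Simulation, 5,000 trials per setting: 6 or 12 participants, latent speed mean 0.2 and SD 0.2, unable below 0.05, change SD 0.08, mean change 0.02, 0.05 or 0.10. About 9–12% of participants change ability. The table shows how often the sign disagrees with the zero-scored mean change.

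| Mean change | Complete pairs | Available-value medians |
|---|---|---|
| 0.02 | 8–9% | 33% |
| 0.05 | 2–3% | 21–23% |
| 0.10 | 0–0.2% | 10–12% |

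The median column also contains ordinary disagreement between a median and a mean.

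**The case against.** The documents are silent; no sentence excludes non-completers. The 10MWT is called a measure of gait speed, so an analyst could enter 0 m/s without contradicting the text. That is true, but nothing requires it. A TUG recorded as a time has no natural value for inability, and the working above gives no TUG figure.

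A reader might infer that the plan drops exactly those who gain or lose walking. That fits only the protocol's paired t-test. The SAP's rank-sum test keeps the one visit that has a value, and the resulting fault is a comparison of partly different people.

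A reader might also infer that the whole functional-recovery result can be reversed. There is no single such result: Table 1 lists seven measures and none is primary. The FIM gait score, which has a level for non-walkers, and WISCI-II are rated off the device in the same people and may register gained or lost walking. This limits the damage, but the two timed tests can still be reported on their own.

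Nor is it shown that a significant result is hidden: the gain example goes from p = 0.65 to 0.07. With the same sets of changes on two assumed sets of baseline speeds (0.1–0.5 and 0.2–0.6 m/s), no version of the SAP's rank-sum test reached p < 0.05 (range 0.17 to 1.0). Spurious significance is therefore shown for the protocol's test and not for the SAP's; what the SAP's test shows is a misleading shift in the medians. All these limits stand.

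**Conclusion.** The concern holds for off-device 10MWT and TUG in poorly-ambulatory participants. The plan foresees people who may not complete the tests, sets no value for that event, and names two analyses that each mishandle it when run on measured values alone. The two results can be biased. In a small group they can change sign or, under the paired t-test, appear significant when they would not if everyone were counted. Reversal is a possibility: with complete pairs it needs a small or opposite change among those who walk at both visits, and in the simulation it was rare at a mean change of 0.10 m/s. The true frequency is unknown, because the documents give neither the number of poorly-ambulatory participants nor any rate of ability change. The SAP should be corrected on this point; the rest of the functional-recovery assessment is not overturned by it.

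**What to change.** State in the SAP, for the off-device tests:

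- **10MWT:** analyse as speed, with 0 m/s when the participant attends but cannot complete it.
- **TUG:** give non-completion one common value worse than any observed time, for example reciprocal time with 0 for unable. Then unable to able counts as improvement, able to unable as worsening, and unable at both visits as no change. A tied worst rank alone does not define a paired difference, so this comparison must be written down.
- **Test:** use a within-person test (signed-rank or sign test, chosen in advance) in place of the rank-sum for these two measures.
- **Missing data:** keep missed visits as missing, separate from inability.
- **Reporting:** give the numbers moving from unable to able and from able to unable, beside the FIM gait score and WISCI-II.

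The cost is one completion-status field per test, a change from the SAP's named test, and a less direct summary than median seconds. The SAP is written in the past tense, so this may have to be a re-analysis. That is feasible only if source records distinguish inability from a missed visit. No treatment or clinical rule changes.
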